Patients with stroke resulting in hemiparesis and foot drop are affected by gait impairments such as poor symmetry, decreased velocity, and decreased endurance. AFOs have been shown to be an effective intervention for improving gait parameters in individuals who are in the chronic stage of stroke recovery (Tyson, Sadeghi-Demneh, & Nester, 2013; Tyson & Kent, 2013). Although, the majority of gait improvements occur within six months of stroke (Kwakkel, Kollen, & Lindeman, 2004), the effect of early bracing with different types of AFOs on gait outcomes has not been investigated thoroughly.

Purpose of the study:

The purpose of this study will be to identify whether patients in the subacute stage of stroke, who demonstrate foot drop, will have better gait outcomes when using a Double Adjustable AFO, or a Posterior Leaf Spring AFO. A secondary purpose will be to determine whether one week of practice significantly changes gait outcomes with either of the AFO conditions.

Research Hypotheses

The research hypotheses of this study are as follows:

1. There will be a difference in gait endurance measurements, gait symmetry measurements and gait velocity measurements at baseline when using custom Double Adjustable AFO compared to a PLS AFO in patients in subacute stage of stroke.
2. There will be a difference in gait endurance measurements, gait symmetry measurements and gait velocity measurements after one week of practice when using custom Double Adjustable AFO compared to a PLS AFO in patients in subacute stage of stroke.
3. After a week of practice, there will be a difference in gait endurance measurements, gait symmetry measurements and gait velocity measurements compared to baseline measurements, when using either custom Double Adjustable AFO or a PLS AFO in patients in subacute stage of stroke.

Significance of Study

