data including age, height, weight, leg length measurements on each side, and Fugl-Meyer Lower Extremity Assessment of sensorimotor function. Then the gait outcomes will be measured using one of the two AFO conditions in random order. Two possible orders will be written on piece of paper and an equal number of possible order selections will be put in a hat. The participant will select the order of AFO condition by drawing out of a hat. Randomization without replacement will be used. Once the order of AFO wearing has been determined, data will be collected in the randomly selected order. Participants will be allowed to use any type of assistive device of their choice, but the same device will be used for all conditions.

First, the 6MWT will be administered with the participant wearing the first randomized AFO. Participants will be asked to ambulate as far as possible in 6 minutes at a self-selected walking velocity through a well-lit indoor corridor. A five minute seated resting will be provided before the next measurement is taken. Next, gait symmetry and gait velocity measurements will be obtained using the GAITRite system. Participants will be given a practice trial walk prior to beginning of the testing. Participants will be asked to walk at their comfortable self-selected walking velocity along the walkway. They will begin walking three meters from the start of the walkway and will stop walking two meters past the end of the walkway. The beginning and end of the walking area will be marked with red tape for visibility. The verbal instruction will be “Please walk from this red line to that red line at your comfortable speed safely”. A second personnel will be walking close to the participant outside of the walkway to ensure safety. After a five minute sitting break, participant will be asked to walk as fast as they can safely. The verbal instruction will be “Please walk from this red line to that red line as fast as you can safely”. The GAITRite system will be able to capture both gait symmetry and gait velocity measurements with the same walk. Three trials will be performed of the self-selected velocity walk and fast

paced velocity walk. The calculated mean of the three trials will be used for data analysis. After a 10 minute seated rest break, the second AFO condition will be used and measurements will be repeated in the same order described above.

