To assess the effects of practice on the gait measures, AFO's will be randomized for practice. Participants will be randomized for which AFO they will wear first (the PLS or the DA AFO), by drawing out of a hat. Again randomization without replacement technique will be used. Then the participant will be provided with the selected type of AFO to practice with for the following week using a prescribed wearing schedule. At the end of the one-week practice time, the primary investigator will obtain the same measurements obtained at baseline with the participant wearing the type of AFO that was used to practice the week before. The same testing conditions and order of testing that were used at baseline will be employed. Once measurements are completed, the participant will be provided with the second type of AFO and will be asked to wear for one week using the same prescribed wearing schedule as before. Final measurements will be taken after completion of the one-week practice using the second type of AFO with the same testing conditions and orders. At the conclusion of testing each participant will be asked which AFO they will prefer to use for their daily ambulatory needs for descriptive analysis. All data collected will be de-identified and stored in the Primary Investigator's secure personal computer. Any documents used such as Participant information sheet will be securely locked in a cabinet at Texas Woman's University where only the Primary investigator will have access.

Data Analysis

The following statistics will be calculated using SPSS for Windows. Descriptive statistics will be calculated for all demographic data including age, height, weight, time since onset Fugl Meyer lower extremity assessment score and AFO preference.

Differences in gait endurance will be analyzed using a 2x2 repeated measures ANOVA. Differences in gait symmetry, and gait velocity between the two AFO conditions and two practice conditions will be analyzed using two separate 2x2 repeated measures MANOVA. If assumption of sphericity is not met, Greenhouse-Geisser statistic will be used. An alpha level of .05 will be used to determine significance of differences, with a Bonferroni correction applied as needed to protect against Type I error.

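### The hypotheses on DA versus PLS at baseline (H1) and after one week of practice (H2) have no named test: no standard effect of the planned 2x2 analyses answers either

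*Combined protocol and SAP*

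**What the plan says.** Research Hypotheses fixes a time for each of the first two comparisons. H1 reads "There will be a difference in gait endurance measurements, gait symmetry measurements and gait velocity measurements at baseline when using custom Double Adjustable AFO", against the PLS. H2 covers the same three outcomes, ending with "gait velocity measurements after one week of practice when using custom Double Adjustable AFO compared to a PLS AFO". H3 concerns the change from baseline to one week with either orthosis.

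Data Analysis gives one model per outcome. For the 6-minute walk test (6MWT): "Differences in gait endurance will be analyzed using a 2x2 repeated measures ANOVA". For symmetry and for velocity, each measured at two paces, differences "between the two AFO conditions and two practice conditions will be analyzed using two separate 2x2 repeated measures MANOVA". It adds a sphericity adjustment, an alpha of .05, and significance testing "with a Bonferroni correction applied as needed to protect against Type I error". It names no main effect, interaction, contrast at a given time or follow-up rule as the test of any hypothesis.

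Procedures shows that the two differences are collected differently. At baseline both orthoses are tested in one session, in random order: "After a 10 minute seated rest break, the second AFO condition will be used and measurements will be repeated". After practice, session 2 is done "with the participant wearing the type of AFO that was used to practice the week before", and the other orthosis waits until session 3: "Final measurements will be taken after completion of the one-week practice using the second type of AFO". Which orthosis is practised first is also randomised.

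**The concern.** A 2x2 within-subject analysis reports three effects by default, and an analyst who runs the plan exactly as written gets no test of H1 or of H2. The tests that answer them, and whether they are run regardless of the interaction or only after a significant one, remain open until analysis.

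Two errors of reading become possible. If DA is better only after practice, a significant AFO main effect with a non-significant interaction would usually be read as a difference at both times, and so as support for H1. If the two differences have opposite signs, the main effect can be null although H1 and H2 are both true.

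The baseline difference is same-day. The post-practice difference spans a week in participants who are 4 to 20 weeks after stroke, and the Introduction says that most gait improvement occurs in the first six months. A change between sessions 2 and 3 is therefore plausible, and it bears on how the H2 contrast should be built.

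**Working it through.** **Inputs.** From the documents: n = 20 (Participants), two within-subject factors with two levels each (Experimental design), alpha .05 (Data Analysis). The sample size rests on precedent, with no effect size, SD or power, so there is no plan figure to reproduce. Assumed here: two-sided tests, normal differences, the effect sizes, and the correlation rho between the two differences.

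**Algebra (no assumptions).** Let D0 and D1 be DA minus PLS at baseline and after practice.

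- AFO main effect: A = (D0 + D1)/2
- Interaction: I = (D1 − D0)/2
- H1: D0 = A − I
- H2: D1 = A + I

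Each hypothesis is an equal mix of main effect and interaction, and the practice effect does not enter. A MANOVA applies the same contrasts to a two-pace vector, so the result holds for all three outcomes.

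**Effect only after practice.** Let dz be the mean difference divided by the SD of that difference. A paired test on 19 df has 80% power at dz = 0.660. Set the mean of D0 to 0, that of D1 to 0.660, and both SDs to 1.

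- Main effect: dz = 0.5 × 0.660 / √((1 + rho)/2), which is 0.467, 0.381, 0.339 at rho 0, 0.5, 0.9
- Interaction: dz = 0.660 / √(2(1 − rho)), which is 0.467, 0.660, 1.477

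| rho | 0 | 0.5 | 0.9 |
|---|---|---|---|
| Direct H2 contrast | 80% | 80% | 80% |
| AFO main effect | 51% | 37% | 30% |
| Interaction | 51% | 80% | >99% |
| Main effect significant, interaction not | 25% | 7% | 0% |
| H2 contrast significant, neither of the others | 9% | 4% | 0% |

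The last two rows come from simulation, 100,000 runs per rho.

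**Other settings.**

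- Baseline difference with half the SD of the post-practice one (plausible, being same-day): main effect 71/56/48%; main effect without interaction 13/1/0%.
- Equal effect at both times, equal SDs: main effect dz = 0.660 / √((1 + rho)/2), power 98/90/82%.
- Opposite effects, dz +0.66 and −0.66, rho 0: the main effect rejects in 4.9% of runs (the null rate), the interaction in 98%, the H1 and H2 contrasts in about 80% each.

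**Practice order in the H2 contrast.** Assume 10 participants per order and no carry-over. A shift s between sessions 2 and 3 adds +s to D1 in one order and −s in the other. The mean is unchanged, but the error term grows. For s = 0, 0.25, 0.5 SD of D1, the plain paired test has 80/78/72% power. With order as a factor (18 df) it stays at 80%. The detectable dz moves from 0.660 to about 0.662.

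**Correction.** Two hypotheses × three outcomes = six tests. The two-pace tests use Hotelling T² with F(2, 18) and noncentrality 20 × Δ², where Δ is the Mahalanobis distance. Detectable effects at 80% power, without the order factor:

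| Alpha | 6MWT dz | Two-pace Δ |
|---|---|---|
| .05 | 0.66 | 0.76 |
| .05/3 | 0.78 | 0.89 |
| .05/6 | 0.86 | 0.97 |

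At .05/6, power at dz 0.66 is 52%, against 80% uncorrected.

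**The case against.** The best defence is that little is really missing. The 2x2 model yields both contrasts from the same data. H1 and H2 already state comparator, time and outcomes. With two levels per factor there is nothing to compare pairwise within a main effect, so the Bonferroni clause can be read as anticipating comparisons within levels. This stands in part: the contrasts are largely implied, and the model is sound. But the clause could equally refer to multiple outcomes, and it gives no comparison, trigger or divisor.

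The AFO main effect is also not irrelevant. The stated purpose, which orthosis gives better outcomes, is not tied to a time, and the main effect serves it well when the effect is equal at both times. That stands too.

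The harm is conditional. The 25% needs no baseline effect, uncorrelated differences, equal SDs, and a reader who takes a non-significant interaction as evidence for H1. The documents plan no such reading and give no figure that selects among the settings.

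A reader might infer that the 2x2 analysis is the wrong model, that the trial cannot answer H1 and H2, or that a false claim on H1 is likely. The documents support none of these. Nor is the H2 comparison shown to be biased: practice order is randomised, and the order factor is argued here on precision only.

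**Conclusion.** The concern holds as a gap between hypotheses and tests. Run exactly as written, the plan tests neither H1 nor H2. That follows from algebra and rests on no assumed value. The fault is the unnamed contrast, not the choice of model.

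The size of the consequence does rest on assumptions. Across the settings tried with an effect only after practice, a significant main effect without a significant interaction ranged from 25% down to 0%. The interaction limits the risk, strongly so when the two differences are well correlated, but it is not itself a test of H1 or H2. The plan should be changed, because the stated analysis does not answer two of its three stated hypotheses and the remedy needs no new data.

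**What to change.** In Data Analysis, tie each hypothesis to a test:

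- **H1:** the paired DA-minus-PLS contrast at session 1, with the randomised session-1 test order as a factor.
- **H2:** the paired DA-minus-PLS contrast of the post-practice measurements (sessions 2 and 3), with the randomised practice order as a factor, so that a change between those sessions stays out of the error term.
- **H3:** the practice effect of the 2x2 analysis, kept as its test.
- Use a paired test for 6MWT and a two-pace multivariate test for symmetry and for velocity.
- Treat only the AFO main effect and the interaction as supportive for H1 and H2.
- List before analysis which tests the Bonferroni correction covers. The family is the sponsor's choice.

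Naming the contrasts is a change of wording, with no added visits, measurements or participants, and the order factor costs almost nothing. The real cost lies in the correction: the family chosen sets how large a difference 20 participants can detect, as the last table shows, and the sponsor should see those figures before choosing.
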